#### RTOG/EORTC LATE RADIATION MORBIDITY SCORING SCHEMA

The RTOG/EORTC Late Radiation Morbidity Scoring Schema should be used to assess toxicity at visit 3 and all subsequent follow up visits.

	0	1	2	3	4	5
		(Expected for FoRT)	(Expected for FoRT)	Not exp	pected for FoRT	
SKIN	None	Slight atrophy Pigmentation change Some hair loss	Patch atrophy; Moderate telangiectasia; Total hair loss	Marked atrophy; Gross telangiectasia	Ulceration	
SUBCUTANEOUS TISSUE	None	Slight induration (fibrosia) and loss of subcutaneous fat	Moderate fibrosis but asymptomatic; Slight field contracture <10% linear reduction	Severe induration and loss of subcutaneous tissue; Field contracture >10% linear measurement	Necrosis	
MUCOUS MEMBRANE	None	Slight atrophy and dryness	Moderate atrophy and telangiectasia; Little mucous	Marked atrophy with complete dryness; Severe telangiectasia	Ulceration	DE/
SALIVARY GLANDS	None	Slight dryness of mouth; Good response on stimulation	Moderate dryness of mouth; Poor response on stimulation	Complete dryness of mouth; No response on stimulation	Fibrosis	ATH DIR
SPINAL CORD	None	Mild L'Hermitte's syndrome	Severe L'Hermitte's syndrome	Objective neurological findings at or below cord level treated	Mono-, para-, quadraplegia	ECTLY REI
BRAIN	None	Mild headache; Slight lethargy	Moderate headache; Great lethargy	Severe headaches; Severe CNS dysfunction (partial loss of power or dyskinesia)	Seizures or paralysis; Coma	DEATH DIRECTLY RELATED TO RADIATION LATE
EYE	None	Asymptomatic cataract; Minor corneal ulceration or keratitis	Symptomatic cataract; Moderate corneal ulceration; Minor retinopathy or glaucoma	Severe keratitis; Severe retinopathy or detachment; Severe glaucoma	Panopthalmitis/ Blindness	ADIATION
LARYNX	None	Hoarseness; Slight arytenoid edema	Moderate arytenoid edema, Chondritis	Severe edema; Severe chondritis	Necrosis	LATE
LUNG	None	Asymptomatic or mild symptoms (dry cough); Slight radiographic appearances	Moderate symptomatic fibrosis or pneumonitis (severe cough); Low grade fever; Patchy radiographic appearances	Severe symptomatic fibrosis or Pneumonitis; Dense radiographic changes	Severe respiratory insufficiency/ Continuous O 2 / Assisted ventilation	EFFECTS
HEART	None	Asymptomatic or mild symptoms; Transient T wave inversion & ST changes; Sinus tachycardia >110 (at rest)	Moderate angina on effort; Mild pericarditis; Normal hear size; Persistent abnormal T wave and ST changes; Low ORS	Severe angina; Pericardial effusion; Constrictive pericarditis; Moderate heart failure; Cardiac enlargement; ECG abnormalities	Tamponade/ Severe heart failure/ Severe constrictive pericarditis	

	0	1	2	3	4	5
		(Expected for FoRT)	(Expected for FoRT)	Not exp	pected for FoRT	
OESOPHAGUS	None	Mild fibrosis; Slight difficulty in swallowing solids; No pain on swallowing	Unable to take solid food normally; Swallowing semi- solid food; Dilation may be indicated	Severe fibrosis; Able to swallow only liquids; May have pain on swallowing; Dilation required	Necrosis/ Perforation; Fistula	
SMALL/ LARGE INTESTINE	None	Mild diarrhoea; Mild cramping; Bowel movement 5 times daily; Slight rectal discharge or bleeding	Moderate diarrhoea and colic; Bowel movement >5 times daily; Excessive rectal mucus or intermittent bleeding	Obstruction or bleeding requiring surgery	Necrosis/ Perforation; Fistula	
LIVER	None	Mild lassitude; Nausea, dyspepsia; Slightly abnormal liver function	Moderate symptoms; Some abnormal liver function tests; Serum albumin normal	Disabling hepatic insufficiency; Liver function tests grossly abnormal; Low albumin; Edema or ascites	Necrosis / Hepatic coma or encephalopathy	
KIDNEY	None	Tranient albuminuria; No hypertension; Mild impairment of renal function; Urea 25- 35mg%, Creatinine 1.5-2.0mg%, Creatinine clearance >75%	Persistent moderate albuminuria (2+); Mild hypertension; No related anaemia; Moderate impairment of renal function; Urea >36-60mg%, Creatinine clearance 50-74%	Severe albuminuria; Severe hypertension; Persistent anaemia (<10g%); Severe renal failure; Urea >60mg%, Creatinine >4mg%, Creatinine clearance <50%	Malignant hypertension; Uremic coma/ Urea >100%	
BLADDER	None	Slight epithelial atrophy; Minor telangiectasia (microscopic hematuria)	Moderate frequency; Generalized telangiectasia; Intermittent macroscopic hematuria	Severe frequency and dysuria; Severe generalised telangiectasia (often with petechiae); Frequent hematuria; Reduction in bladder capacity (<150cc)	Necrosis/ Contracted bladder (capacity <100cc); Severe hemorrhagic cystitis	
BONE	None	Asymptomatic; No growth retardation; Reduced bone density	Moderate pain or tenderness; Growth retardation; Irregular bone sclerosis	Severe pain or tenderness; Complete arrest of bone growth; Dense bone sclerosis	Necrosis/ Spontaneous fracture	
JOINT	None	Mild joint stiffness; Slight limitation of movement	Moderate stiffness; Intermitten or moderate joint pain; Moderate limitation of movement	Severe joint stiffness; Pain with severe limitation of movement	Necrosis; Complete fixation	

http://www.rtog.org/members/toxicity/late.html

## APPENDIX 3: RECIST CRITERIA

#### Response Evaluation Criteria in Solid Tumours (RECIST v1.0)

#### **Quick Reference:**

#### **Eligibility**

- Only patients with measurable disease at baseline should be included in protocols where objective tumor response is the primary endpoint.
  - ➤ Measurable disease the presence of at least one measurable lesion. If the measurable disease is restricted to a solitary lesion, its neoplastic nature should be confirmed by cytology/histology.
  - ➤ Measurable lesions lesions that can be accurately measured in at least one dimension with longest diameter ≥20 mm using conventional techniques or ≥10 mm with spiral CT scan.
  - ➤ Non-measurable lesions all other lesions, including small lesions (longest diameter <20 mm with conventional techniques or <10 mm with spiral CT scan), i.e., bone lesions, leptomeningeal disease, ascites, pleural/pericardial effusion, inflammatory breast disease, lymphangitis cutis/pulmonis, cystic lesions, and also abdominal masses that are not confirmed and followed by imaging techniques; and.
- All measurements should be taken and recorded in metric notation, using a ruler or calipers.
   All baseline evaluations should be performed as closely as possible to the beginning of treatment and never more than 4 weeks before the beginning of the treatment.
- The same method of assessment and the same technique should be used to characterize each identified and reported lesion at baseline and during follow up.
- Clinical lesions will only be considered measurable when they are superficial (e.g., skin nodules and palpable lymph nodes). For the case of skin lesions, documentation by color photography, including a ruler to estimate the size of the lesion, is recommended.

#### Response Criteria

#### **Evaluation of target lesions**

\* Complete Response Disappearance of all target lesions

(CR):

(PD):

Partial Response At least a 30% decrease in the sum of the LD of target lesions, taking

(PR): as reference the baseline sum LD

\* Progressive Disease At least a 20% increase in the sum of the LD of target lesions, taking as

reference the smallest sum LD recorded since the treatment started or

the appearance of one or more new lesions

\* Stable Disease (SD): Neither sufficient shrinkage to qualify for PR nor sufficient increase to

qualify for PD, taking as reference the smallest sum LD since the

treatment started

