### 1.5 Relevant studies/trials

Recently published data has shown a high level of durable response with only 4Gy in 2 fractions. In a total of 304 symptomatic sites treated in this way there was an overall response rate of 92% with 61% complete responses and a median time to local progression of 25 months; this was 42 months in those achieving complete responses. A smaller series of 11 patients had previously reported similar success with a 94% response rate of mean duration 7 months using this low dose schedule. This raises the possibility that a dose of 4Gy, given in 2Gy fractions may be effective and potentially more efficient in the use of radiotherapy for indolent lymphoma. It would therefore seem that the next important question in the radiotherapeutic management of indolent lymphoma is the relative efficacy of such an ultra low dose 2 fraction schedules compared with a more conventional fractionated treatment over two to four weeks. Against this background it is therefore proposed that a prospective randomised trial of 4Gy in 2 fractions compared to a standard schedule of 24Gy in 12 fractions is undertaken.

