#### Secondary

Acute toxicity: assessed at the week 4 visit using RTOG Acute Radiation Morbidity Scoring Criteria

Late toxicity: assessed using RTOG/EORTC Late Radiation Morbidity Scoring Criteria or, if the RTOG criteria are not applicable, using the Common Terminology Criteria for Adverse Events v3.0 (CTCAE), available online at:

http://ctep.cancer.gov/protocolDevelopment/electronic\_applications/docs/ctcaev3.pdf

 $\underline{\textit{Response}}$ : assessed at the 12 weeks from randomisation using RECIST criteria

Overall survival: time from randomisation to date of death of any cause

Health economic assessment: details of protocol treatments, other anti-cancer treatments (excluding complementary therapy), management of adverse events, hospital admission episodes, and EQ-5D questionnaire

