#### **Evaluation of best overall response**

The best overall response is the best response recorded from the start of the treatment until
disease progression/recurrence (taking as reference for PD the smallest measurements
recorded since the treatment started). In general, the patient's best response assignment
will depend on the achievement of both measurement and confirmation criteria

Target lesions	Non-Target lesions	New Lesions	Overall response
CR	CR	No	CR
CR	Incomplete response/SD	No	PR
PR	Non-PD	No	PR
SD	Non-PD	No	SD
PD	Any	Yes or No	PD
Any	PD	Yes or No	PD
Any	Any	Yes	PD

- Patients with a global deterioration of health status requiring discontinuation of treatment without objective evidence of disease progression at that time should be classified as having "symptomatic deterioration". Every effort should be made to document the objective progression even after discontinuation of treatment.
- In some circumstances it may be difficult to distinguish residual disease from normal tissue.
   When the evaluation of complete response depends on this determination, it is recommended that the residual lesion be investigated (fine needle aspirate/biopsy) to confirm the complete response status.

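### Appendix 3 sets no size at which an irradiated lymph node counts as complete response, so week-12 CR is understated for CT-followed nodes and depends on the assessment method

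*Protocol*

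**What the plan says.** Section 5.2 of the protocol lists response as a secondary outcome, "assessed at the 12 weeks from randomisation using RECIST criteria". Section 3.8 limits it to disease inside the irradiated field and has sites enter the category on the Tumour Response Evaluation CRF.

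Appendix 3 prints RECIST v1.0. For target lesions the rule is "Complete Response Disappearance of all target lesions". Partial response (PR) needs a fall of at least 30% in the sum of longest diameters from baseline. A smaller fall, short of progression, is stable disease (SD). CR for non-target lesions also requires disappearance. Neither rule has a nodal size. The only sizes in the appendix are measurability limits: non-measurable disease includes "small lesions (longest diameter <20 mm with conventional techniques or <10 mm with spiral CT scan".

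For doubtful cases the appendix notes: "In some circumstances it may be difficult to distinguish residual disease from normal tissue". Where CR turns on that judgement, it recommends that "the residual lesion be investigated (fine needle aspirate/biopsy) to confirm the complete response status".

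On method, section 3.8 accepts clinical measurement or examination, x-ray or CT. It asks for a repeat CT at 12 weeks when intent is curative. For palliative intent, imaging is left to clinical indication. Lesion dimensions are recorded if they are available. Appendix 3 counts palpable nodes as measurable clinical lesions and asks for the same method at baseline and follow-up.

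**The concern.** Section 1.4.1 describes the palliative targets as nodal or extranodal masses, so many target lesions will be lymph nodes. A node is normal anatomy. When the tumour in it resolves, it may return to normal size and still be visible on CT. A rule that demands disappearance cannot score that outcome as CR, although an extranodal lesion that clears to the same degree does score CR.

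Two things are at stake. The recorded CR rate would be too low wherever nodes are followed on CT. CR would also mean different things in different patients, according to how they were assessed. A later analysis plan could not reliably repair this, because the site applies the rule on the CRF and node dimensions may be absent.

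**Working it through.** **The plan's own figures.** The protocol states no power or sample size for response. Its only sample-size figures (Table 2) concern local progression free interval, and they reproduce. For 50% v 40%, HR 1.32, one-sided 5% and 90% power, events = 4(1.645 + 1.282)² / (ln 1.32)² = 445, against 446 stated. Dividing 446 by the mean event probability of the two arms (exponential, 4-year accrual plus 1 year: 0.664) gives 672 patients, against 671. Response does not enter this calculation.

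**Step 1: apply the printed rule to single CT-followed nodes (illustrative sizes).**
- 40 mm to 8 mm: (40 − 8)/40 = 80% fall, node still visible, scored PR. The residual 8 mm is below the appendix's 10 mm limit for a measurable lesion on spiral CT.
- 30 mm to 15 mm: 50% fall, PR.
- 20 mm to 15 mm: 25% fall, SD. If 15 mm were normal for that node, this case would lower CR + PR as well as CR.
- A node followed by palpation and no longer felt has disappeared by that method, so it can be CR.

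**Step 2: effect on the CR rate.** Let p be the true CR rate and f the fraction of true CRs scored lower. Then recorded CR = p(1 − f). Here f is the share of true CRs that are CT-followed nodes multiplied by the share of those that stay visible. The protocol gives neither share.

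The only CR rate in the document is 61% at 4Gy (section 1.5: "there was an overall response rate of 92% with 61% complete responses"). It serves here as a stand-in for p. The 24Gy rate of 71% and every f are assumptions. With 650/2 = 325 per arm and a two-sided 5% test (assumed), power = Φ{[d − 1.96√(2p̄(1 − p̄)/n)] / √[(p₁q₁ + p₂q₂)/n]}, where p₁ and p₂ are the recorded CR rates, q = 1 − p, p̄ is their mean, d their difference and n = 325. With equal f in both arms:

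| f | CR 24Gy | CR 4Gy | Difference (points) | Power |
|---|---|---|---|---|
| 0 | 71.0% | 61.0% | 10.0 | 77% |
| 0.1 | 63.9% | 54.9% | 9.0 | 65% |
| 0.2 | 56.8% | 48.8% | 8.0 | 53% |
| 0.3 | 49.7% | 42.7% | 7.0 | 43% |
| 0.5 | 35.5% | 30.5% | 5.0 | 27% |

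The ratio of CR rates stays at 0.71/0.61 = 1.16 throughout.

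**Step 3: unequal f.** Recorded difference = true difference − (p₂₄f₂₄ − p₄f₄). The 10 points fall only if p₂₄f₂₄ exceeds p₄f₄.
- f₂₄ = 0.2, f₄ = 0.1: 56.8 − 54.9 = 1.9 points.
- f₂₄ = 0.2, f₄ = 0.233 (that is, 0.71 × 0.2/0.61): 56.8 − 46.8 = 10.0 points, unchanged.
- f₂₄ = 0.1, f₄ = 0.2: 63.9 − 48.8 = 15.1 points.

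**Step 4: can f differ by arm?** Randomisation is stratified by intent (section 5.1), so the curative/palliative difference in imaging should be balanced between arms. Within the palliative stratum, however, imaging is decided as follow-up proceeds, with the allocation known (open design, section 1.2). Equal f therefore cannot be taken for granted.

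**The case against.** **The appendix already covers the doubtful case.** It recommends aspirate or biopsy where residual tissue and disease cannot be told apart, and a conditional test need not appear in the visit schedule. This stands in part: a CR can be confirmed despite a residual lesion. But the step is only recommended, and section 3.8 does not mention it in the week-12 assessment. Where it is not done, the literal rule decides.

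**Palpated nodes escape the problem, and extranodal lesions are unaffected.** This stands. It confines the understatement to CT-followed nodes, and an f of 0.2 to 0.5 across all patients may be high. It also exposes the dependence on method. The same-method instruction limits switching within a patient, but it does not make CR mean the same thing in different patients.

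**Measurable is not the same as normal.** This stands. The 10 mm CT limit says what can be measured accurately. It is no evidence of a normal-node cut-off.

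**Response is an unpowered secondary outcome and CR v non-CR is not its fixed contrast.** This stands. Section 5.4 allows chi-squared or Mann-Whitney tests, so the power column above is only an illustration.

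Three stronger readings are tempting, and the documents do not support them:
- *The arm difference necessarily shrinks, which favours non-inferiority.* Step 3 shows that it can shrink, stay the same or widen. The 10-point margin belongs to local progression free interval, not to response.
- *The 20% progression rule, with no minimum in millimetres, adds false events to the primary endpoint.* Section 5.2 defines primary progression by clinical examination and imaging. RECIST is tied to week 12, and serial millimetre CT readings are not scheduled.
- *Recorded CR cannot be compared with the published 61%.* Section 1.5 does not say which criteria that series used, so this cannot be judged either way.

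**Conclusion.** The point holds for CR within the week-12 response outcome. Appendix 3 states a rule that, followed literally, scores a CT-followed node of normal size as PR or SD, while the same node assessed by palpation can be CR. CR is understated by the factor (1 − f) overall, and its meaning varies with method and so with treatment intent. At assumed f of 0.1, 0.2 and 0.3, a true 61% is recorded as 55%, 49% and 43%.

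The bias in the difference between arms is unknown in both direction and size. Under an assumed true 71% v 61%, the 10 points become 5 to 9 with equal f of 0.5 to 0.1, and 1.9 to 15.1 in the unequal examples. The 24Gy rate and all f are assumptions. Local progression free interval and Table 2 are not affected. The repair is cheap enough that it should be made.

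**What to change.** Before response is analysed, add one nodal rule for CR to Appendix 3 and the CRF guidance, applied identically in both arms:
- For a node followed on CT, count CR when it is below a stated size. The trial team should choose and justify that size in advance, without reference to outcome by arm.
- For a node followed clinically, count CR when it is not palpable as enlarged.
- For extranodal lesions, keep disappearance.
- At week 12, record the assessment method and, for CT-followed nodes, the residual size whenever the node is still visible.

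The cost is wording in the appendix and CRF guidance, plus at most two CRF fields. No scan, visit or biopsy is added. The downside is that some normal-size nodes with residual disease would count as CR. For patients already assessed, the rule can be applied only where dimensions were recorded, and the number without them should be reported by arm.

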#### Evaluation of non-target lesions

\* Complete Response Disappearance of all non-target lesions and normalization of tumor

(CR): marker level

\* Incomplete Persistence of one or more non-target lesion(s) or/and maintenance of

Response/ Stable tumor marker level above the normal limits

Disease (SD):

\* Progressive Disease Appearance of one or more new lesions and/or unequivocal

(PD): progression of existing non-target lesions (1)

Although a clear progression of "non target" lesions only is exceptional, in such circumstances, the opinion of the treating physician should prevail and the progression status should be confirmed later on by the review panel (or study chair).

#### **Evaluation of best overall response**

The best overall response is the best response recorded from the start of the treatment until
disease progression/recurrence (taking as reference for PD the smallest measurements
recorded since the treatment started). In general, the patient's best response assignment
will depend on the achievement of both measurement and confirmation criteria

Target lesions	Non-Target lesions	New Lesions	Overall response
CR	CR	No	CR
CR	Incomplete response/SD	No	PR
PR	Non-PD	No	PR
SD	Non-PD	No	SD
PD	Any	Yes or No	PD
Any	PD	Yes or No	PD
Any	Any	Yes	PD

- Patients with a global deterioration of health status requiring discontinuation of treatment without objective evidence of disease progression at that time should be classified as having "symptomatic deterioration". Every effort should be made to document the objective progression even after discontinuation of treatment.
- In some circumstances it may be difficult to distinguish residual disease from normal tissue.
   When the evaluation of complete response depends on this determination, it is recommended that the residual lesion be investigated (fine needle aspirate/biopsy) to confirm the complete response status.

# **APPENDIX 4: FOLLOW UP SCHEDULE**

Table 3 shows the visit schedule for the FoRT trial

Table 3: FoRT trial visit schedule

Visit number	Timepoint
1	Baseline
2	4 weeks post randomisation
3	12 weeks post randomisation – response assessment
4	6 months post randomisation
5	1 year post randomisation
6	18 months post randomisation
7	2 years post randomisation
8	3 years post randomisation
9	4 years post randomisation
10	5 years post randomisation

Once the five years of scheduled follow up are completed, patients will be followed up for survival annually until death.

The forms due at each visit are summarised in table 4 below.

Table 4: Forms due at each clinic visit

Form	Details	Compulsory / as required
Registration form	4 pages to be completed at visit 1 and faxed to UCL CTC	Compulsory
Randomisation form	1 page to be completed at visit 1 and faxed to UCL CTC	Compulsory
4-week follow up form	1 page to be posted to UCL CTC within 8 weeks of visit 2	Compulsory
Acute toxicity form	1 page to be posted to UCL CTC to be completed at visit 2 as required and posted to the UCL CTC within 8 weeks of visit 2 along with 4-week follow up form	Only required if patient experienced acute toxicity from radiotherapy
12-week follow up form	4 pages to be posted to UCL CTC within 8 weeks of visit 3	Compulsory
Follow up form	1 page to be completed at visits 4 – 10 and posted to UCL CTC within 8 weeks of visit	Compulsory up to the point of local progression
Late toxicity form	1 page to be completed at visit 3 – 10 as required and posted to UCL CTC within 8 weeks of the relevant visit along with the follow up form	Only required if patient experienced late toxicity from radiotherapy
Disease progression form	1 page to be completed at first progression within the irradiated field	Only required at local progression
Disease progression follow up form	1 page to be completed at all scheduled visits after local progression instead of the follow up form	Compulsory after local progression
Anti-cancer treatment form	1 page to be completed at visits 2-10 as required and posted to UCL CTC within 8 weeks of the relevant visit along with the follow up form	Only required if patient received cancer treatment other than their trial radiotherapy
Hospital admission form	1 page to be completed at visits 2-10 as required and posted to UCL CTC within 8 weeks of the relevant visit along with the follow up form	Only required if patient is admitted to hospital
Withdrawal from treatment	1 page to be completed at visit 2 if required and posted to UCL CTC within 8 weeks of visit 2 along with the 4-week follow up form	Only required if patient fails to complete their randomised radiotherapy
Withdrawal of consent	1 page to be completed at any visit if the patient withdraws consent to the trial. To be posted to UCL CTC immediately	Only required if patient withdraws consent to the trial
Patient death	1 page to be completed as soon as the site is aware of a patient dying. To be posted to UCL CTC immediately	Only required if patient dies
EQ-5D Health Questionnaire	Patient to complete this questionnaire at every trial visit. To be posted to UCL CTC with a coversheet indicating the patient's details and visit number within 8 weeks of the relevant visit.	Compulsory

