### 3.9 Procedures for assessing safety

Acute toxicity will be determined at 4 weeks post randomisation using the RTOG Acute Radiation Morbidity Scoring Schema (Appendix 2). The late toxicity will then be assessed at every visit thereafter using the RTOG/EORTC Late Radiation Morbidity Scoring Schema (Appendix 2). See section 6 on Safety Reporting for more information.

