### Adverse Event (AE)

Any untoward medical occurrence or effect in a patient treated on a trial protocol, which does not necessarily have a causal relationship with this treatment. An AE can therefore be any unfavourable and unintended sign (including an abnormal laboratory finding), symptom or disease temporally associated with the use of the trial treatment, whether or not related to the trial treatment.

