## **Reporting Procedures**

### **All Adverse Events (AEs)**

All adverse events that occur between informed consent and the end of the trial must be recorded in the patient notes and the trial CRFs. Information regarding dates of event onset and resolution, outcome, severity and causality for the trial treatment must be recorded. Those meeting the definition of a Serious Adverse Event (SAE) must also be reported to the UCL CTC using the trial specific SAE Report (see Serious Adverse Events section for details).

Pre-existing conditions do not qualify as adverse events unless they worsen.

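### Table 4 returns the toxicity forms only when an open-label site attributes toxicity to radiotherapy, while section 6 requires all adverse events on the CRFs, related or not

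*Protocol*

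**What the plan says.** Table 4 (Appendix 4) lists the acute toxicity form for visit 2 and the late toxicity form for visits 3 to 10, each as required. The condition for the acute form is "Only required if patient experienced acute toxicity from radiotherapy" and for the late form "Only required if patient experienced late toxicity from radiotherapy".

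Three other parts of the protocol bear on this:

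- **Assessment.** Section 3.9 states: "Acute toxicity will be determined at 4 weeks post randomisation using the RTOG Acute Radiation Morbidity Scoring Schema". It continues: "The late toxicity will then be assessed at every visit thereafter". Appendix 2 says that the late scale "should be used to assess toxicity at visit 3 and all subsequent follow up visits". Both scales include grade 0.
- **Adverse event recording.** Section 6 states: "All adverse events that occur between informed consent and the end of the trial must be recorded in the patient notes and the trial CRFs". Severity and causality are among the items to be recorded for each event. Its definition of an adverse event covers anything temporally associated with treatment, "whether or not related to the trial treatment".
- **Use of the data.** Section 5.2 names acute and late toxicity as secondary outcomes, and section 5.4 compares toxicity between arms by chi-squared or Mann-Whitney tests. Section 1.2 describes the study as open.

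**The concern.** Section 6 treats causality as something to write down about an event. Table 4 uses it to decide whether the toxicity form is sent. If sites follow Table 4 as written, an event judged unrelated to radiotherapy produces no toxicity form, and Table 4 offers no other form for it unless it leads to a hospital admission. That judgement is made by staff who know the allocation, in a trial where the two schedules differ sixfold in dose. A belief that 4Gy cannot cause a symptom, or that 24Gy probably did, would then affect which records exist and not only how they are labelled.

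There is a second gap. On the toxicity forms alone, three situations look the same: scored and found to be grade 0, not scored, and scored with toxicity but the form lost. A between-arm test needs a known grade for each assessed patient. An analysis plan can choose how to treat an absent form, but it cannot recover a grade that was never collected.

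**Working it through.** The protocol gives no toxicity rate, form-return rate or power for toxicity, so there is no stated figure to reproduce. The check is a comparison of the texts, followed by an illustration on assumed rates.

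**Comparison of the texts**

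| Question | Section 6 | Table 4 |
|---|---|---|
| Which events reach the CRF? | All, from consent to end of trial | Toxicity forms only for toxicity due to radiotherapy |
| Role of causality | A recorded item | The condition for returning the form |
| Non-serious event judged unrelated | Must be on the CRF | No form named, unless the patient is admitted |
| Visit with no toxicity | Not addressed | No toxicity form |

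The late form is to be posted with the follow up form. That form is compulsory only until local progression, when the disease progression follow up form replaces it. Even if the follow up form held a toxicity item, nothing says that its replacement does.

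**Illustration**

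Let p be the true proportion with toxicity. Let f be the share of those patients for whom no form arrives, whether lost or withheld on attribution. If an absent form were read as no toxicity, the observed proportion would be q = p(1 − f). All p and f below are assumptions.

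- True 30% (24Gy) v 10% (4Gy), f = 10% in both arms: 0.30 × 0.90 = 0.27 and 0.10 × 0.90 = 0.09. The difference is 18 points instead of 20.
- Same true rates, f = 20% v 5%: 0.30 × 0.80 = 0.24 and 0.10 × 0.95 = 0.095. The difference is 14.5 points instead of 20.
- True 20% v 10%, f = 10% v 30%: 0.20 × 0.90 = 0.18 and 0.10 × 0.70 = 0.07. The difference is 11 points instead of 10, so the bias can also favour 4Gy.
- True 20% in both arms, f = 10% v 30%: 0.20 × 0.90 = 0.18 and 0.20 × 0.70 = 0.14. A difference of 4 points appears where there is none.

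For the last case, take 325 per arm (650 at 1:1, section 5.3) and a two-sided 5% test with pooled null variance:

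- pooled proportion = (0.18 + 0.14)/2 = 0.16
- null SE = √(2 × 0.16 × 0.84/325) = 0.02876
- SE under the observed rates = √((0.18 × 0.82 + 0.14 × 0.86)/325) = 0.02872
- probability of rejection = Φ((0.04 − 1.96 × 0.02876)/0.02872) = Φ(−0.57) ≈ 0.28, against a nominal 0.05

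The same calculation for true rates of 20% v 10% gives power of 0.95 with complete return, 0.88 when 20% of forms are missing in both arms (16% v 8%), and 0.52 when 30% are missing on 24Gy and 10% on 4Gy (14% v 9%).

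With f = 0 in both arms, q = p and there is no bias.

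**The case against.** The case on the other side has several parts.

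- **Section 3.9.** A reader might infer that Table 4 directly contradicts 3.9. It does not. Section 3.9 governs assessment and Table 4 governs which page is posted, so scoring everyone and sending a page only for positives is consistent. This objection stands in full.
- **Core forms.** Every visit after baseline has a compulsory form, and the toxicity page is sent alongside it. A core form with trigger questions and supplementary pages would fit this layout. It would also separate a missed visit from a visit without toxicity, and a yes/no item would expose a lost page. This may be the actual CRF design, but the protocol does not say so.
- **Absent read as none.** A reader might infer that unreturned forms will be counted as grade 0. Nothing in the protocol says that. How absent forms are analysed, including any restriction to patients with a returned form, belongs to the analysis plan and is not criticised here.
- **Attribution.** The RTOG scales grade radiation morbidity, and the guidance in Appendix 2 already asks the evaluator to separate disease effects from treatment effects. Compulsory forms would not remove that judgement. They would, however, make it visible in the data.
- **Completeness of Table 4.** It is a summary of forms due at visits and omits the SAE and pregnancy reports, so an adverse event form might exist elsewhere. The protocol names none. SAE reporting covers serious events to 30 days after treatment and later ones thought related, but it does not cover non-serious events.
- **Importance.** A reader might infer that toxicity carries much of the argument for 4Gy. Section 1.6 argues mainly from radiotherapy resources and the need to justify exposure, and section 5.3 sets the aim as non-inferiority on local progression. Toxicity is secondary.

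**Conclusion.** The point holds as a mismatch between Table 4 and section 6. The forms that carry two secondary outcomes depend on an attribution made with knowledge of the arm, whereas section 6 wants all events on the CRFs with causality recorded. No form is named for non-serious events judged unrelated. The protocol also does not say where absence of toxicity is positively recorded.

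The size of any bias is unknown, because the protocol gives neither toxicity rates nor return rates. The illustration shows only that incomplete return or uneven attribution could shrink, enlarge or create a difference. It assumes that absent forms are read as no toxicity, which the protocol does not state. The primary outcome is not affected. The change is worth making because it is cheap and the missing grades could not be recovered later.

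**What to change.** 1. In Table 4, make the acute form compulsory at visit 2 and the late form compulsory at visits 3 to 10, including visits after local progression, with grade 0 entered where there is no toxicity. Alternatively, add a compulsory toxicity item that allows grade 0 to the core form at each of these visits, including the disease progression follow up form. If the core forms already carry such an item, say so in Table 4.
2. Record each event with its grade and a separate relatedness field, and stop using attribution as the condition for returning the form. The judgement that Appendix 2 asks of the evaluator then goes into that field.
3. Name the CRF on which non-serious events judged unrelated are recorded, so that Table 4 agrees with section 6.
4. Report the number of missing toxicity forms by arm and visit.

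The cost is one more CRF page or item at visits without toxicity. No visits or procedures are added.
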